### **Laboratory Test Results**

In addition to the recording specified above, the following laboratory test results will be entered into the relevant infant laboratory eCRFs, regardless of whether the test was protocol-specified or ordered by the site investigator for clinical purposes:

- All HIV test results
- All creatinine results regardless of severity grade
- All results that are serious as defined in Version 2.0 of the DAIDS EAE Manual

## **7.3 Expedited Adverse Event (EAE) Reporting**

EAEs will be reported only for participants in this study who are exposed to study drug.

### **7.3.1 Adverse Event Reporting to DAIDS**

Requirements, definitions, and methods for expedited reporting of adverse events (AEs) are outlined in Version 2.0 of the DAIDS EAE Manual, which is available on the RSC website at <https://rsc.niaid.nih.gov/clinical-research-sites/manual-expedited-reporting-adverse-events-dais>.

The DAIDS Adverse Experience Reporting System (DAERS), an internet-based reporting system, must be used for EAE reporting to DAIDS. In the event of system outages or technical difficulties, EAEs may be submitted via the DAIDS EAE Form. This form is available on the DAIDS RSC website at <https://rsc.niaid.nih.gov/clinical-research-sites/paper-eae-reporting>

For questions about DAERS, please contact NIAID Clinical Research Management System Support via email at [[contact]](mailto:[contact]). Site queries may also be sent from within the DAERS application itself.

For questions about expedited reporting, please contact DAIDS RSC Safety Office via email at [[contact]](mailto:[contact]).

### **7.3.2 EAE Reporting Requirements for this Study**

- EAEs will be reported only for maternal and infant participants in this study who are exposed to study drug.
- The serious adverse event (SAE) reporting category, as defined in Version 2.0 of the DAIDS EAE Manual, will be used for this study.
- The study agent for which expedited reporting is required is FTC/TDF.

### 7.3.3 Grading Severity of Events (applies to EAEs and all other adverse events)

The Division of AIDS Table for Grading the Severity of Adult and Pediatric Adverse Events (DAIDS AE Grading Table), Corrected Version 2.1, dated July 2017 will be used in this study. This table is available on the RSC website at: <https://rsc.niaid.nih.gov/clinical-research-sites/daids-adverse-event-grading-tables>. For maternal participants in the PrEP Comparison Component, grading of creatinine and CrCl should be based on absolute value only, not on percentage change from baseline. In addition, the following protocol-specific grading scheme for axillary-measured fever will be used in this study:

Grade 1	37.4 to <38.0°C
Grade 2	38.0 to <38.7°C
Grade 3	38.7 to <39.4°C
Grade 4	≥39.4°C

*Note: The DAIDS AE Grading Table parameter for unintentional weight loss excludes postpartum weight loss. Therefore, maternal weight loss will not be graded in this study.*

### 7.3.4 EAE Reporting Period

For maternal and infant participants exposed the study drug, the EAE reporting period begins at first exposure to study drug and ends on the date of last exposure to study drug.

For mothers, exposure to study drug is based on ingestion of FTC/TDF. The EAE reporting period begins on the day of first FTC/TDF tablet ingestion and ends on the last day of FTC/TDF tablet ingestion.

For infants, exposure to study drug may occur *in utero* and/or through breast milk while the mother is taking FTC/TDF. The EAE reporting period begins on the day of the first exposure *in utero* or through breast milk and ends after the day of last exposure *in utero* or through breast milk. For example, for an infant whose mother takes FTC/TDF during pregnancy but not postpartum, the infant's EAE reporting period would begin on the day of the mother's first FTC/TDF tablet ingestion during pregnancy and ends after delivery. For an infant, whose mother takes FTC/TDF during pregnancy and postpartum, and breastfeeds the infant, the infant's EAE reporting period would begin on the day of the mother's first FTC/TDF tablet ingestion during pregnancy and end after the mother's date of last FTC/TDF tablet ingestion.

After the above-specified period, only suspected, unexpected, serious adverse reactions (SUSARs), as defined in Version 2.0 of the DAIDS EAE Manual, will be reported to DAIDS if the study staff become aware of such events on a passive basis (e.g., from publicly available information).

## 8 PARTICIPANT MANAGEMENT

### 8.1 Maternal and Infant Adverse Events

All maternal and infant adverse events identified in this study will be source documented in participant research records, consistent with the policies and procedures referenced in [Section 11](#). Among other details, source documentation will include the severity of each event (graded as

described in [Section 7.3.3](#)) and its relationship to study drug assessed by the site clinician according to the following categories and definitions:

**Related:** There is a reasonable possibility that the AE may be related to FTC/TDF

**Not related:** There is not a reasonable possibility that the AE is related to FTC/TDF

Maternal participants who choose to take PrEP are considered exposed to study drug immediately after initiation of dosing through ingestion of the last dose of study drug. Infant participants are considered exposed to study drug *in utero* and through breast milk, if their mothers choose to take PrEP and to breastfeed. Infant exposure begins immediately after initiation of maternal dosing and ceases following ingestion of the last maternal dose of study drug or breast milk feed (or after birth, if not breastfed).

All adverse events must be followed to resolution (return to baseline) or stabilization, with the frequency of repeat evaluations determined by the clinical significance of each event. Additional evaluations beyond those listed in the Schedule of Evaluations may be performed at the discretion of the site investigator to determine the etiology of a given event and/or further assess its severity or relationship to study drug. Clinical management of all adverse events should be provided consistent with the best medical judgment of the site investigator and local clinical practice standards.

### **8.1.1 Management of Maternal Adverse Events**

Maternal adverse events will be managed based on their severity and assessed relationship to study drug. Refer to management table in [Appendix V](#) for detailed guidance on management of reduced creatinine clearance. All other adverse events should be managed as shown in [Appendix IV](#) for general toxicities. Site investigators will consult with the CMC as directed in the Maternal Toxicity Management Tables in [Appendices IV](#) and [V](#) and otherwise at their discretion as needed. The protocol Clinical Management Committee (CMC) will be notified of all events resulting in a change in the administration of the study drug. Clinical or laboratory AEs that are not related to FTC/TDF need not result in study drug interruption, unless the site investigator deems interruption necessary due to the specific circumstances. All maternal participants will remain on study and complete all follow-up visits, even if FTC/TDF is discontinued early due to toxicity or other reasons. Maternal participants with an ongoing AE at the time of the End of Study visit of Grade 3 or higher will continue to be followed until resolution or stabilization of the event. The CMC may request additional follow-up of selected AEs of lower grade based on the clinical context.

For maternal participants with other ongoing adverse events at End of Study visit, sites will continue to manage these conditions per local guidelines until the participant has been transitioned to a non-study primary care provider for continued monitoring, care and treatment. For adverse events of any severity assessed to be related to study-supplied study drug FTC/TDF that are ongoing at week 26 postpartum, sites will inform the CMC of their plan for continued clinical management

### **8.1.2 Compromised Renal Function**

Further action is required if reduced creatinine clearance is recorded at any time during follow-up to evaluate potential compromise of a maternal participant's renal function. [Appendix V](#) provides general guidance for management of the FTC/TDF in response to reduced creatinine clearance.

### **8.1.3 Maternal Bone Mineral Density Concerns**

There is no clarity on which bone density normative ranges should apply to women in Sub-Saharan Africa, given that available data suggests American Caucasian reference ranges are not appropriate and there are no accepted normative ranges for the region. Additionally, the degree of bone lost during periods of lactation is highly variable and maternal participants are likely to continue lactating for several months' post study exit. Thus, bone density scans conducted in this setting after delivery and prior to breastfeeding cessation are difficult to interpret clinically for the individual woman. Hence, maternal DXA scan data obtained in this study will only be of use for research purposes alone. The site investigator may specifically request these data for an individual participant at their discretion.

### **8.1.4 Infant Bone Mineral Density Concerns**

There are no normal ranges for infant bone mineral content in current use. Infant DXA scan data obtained for this study are for research purposes alone and are not readily interpreted for clinical use. If normal values for infants become established while implementing this protocol, the DXA results will be communicated to the site investigator who will use his or her clinical judgment regarding medical consultation and referral.

## **8.2 Management of Participants Who Become Pregnant on Study**

Pregnancy testing will be performed according to the relevant Schedule of Evaluations and when clinically indicated at any time during maternal follow-up and participants will be provided with contraception counseling per local standards of care, see [Section 3.3](#).

Participants enrolled in Group 2 of the PK Component or in the PrEP Comparison Component who become pregnant during the study will be maintained in follow-up through scheduled study exit with no change to their study drug regimen. When the new pregnancy is identified, participants in Cohort 2 of the PrEP Comparison Component will be offered PrEP; if they choose to start PrEP, they will enter Cohort 2/Step 2 (see [Section 5.1](#)). Given that these participants will exit the study prior to delivery, those receiving PrEP will be referred to standard of care maternity services and efforts will be made to transition participants to locally available sources of PrEP to avoid gaps in PrEP coverage.

Participants who are pregnant at the time of study exit, will be contacted by study staff to ascertain their pregnancy outcomes (completion/termination of the pregnancy) and this information will be entered onto eCRFs. Outcomes may be ascertained based on participant report but medical records should be obtained whenever possible to supplement these reports.

## **8.3 Criteria for Premature Discontinuation of Study Drug**

Study drug will be permanently discontinued before study exit in the following scenarios:

- Confirmed maternal HIV infection
- Confirmed maternal Grade 4 laboratory abnormality related to study drug
- Confirmed maternal Grade 3 laboratory abnormality related to study drug that does not resolve to Grade 2 or lower within 14 days of study drug hold
- Confirmed maternal Grade 3 or higher laboratory abnormality or clinical AE that recurs during re-challenge with the study drug after a hold
- Confirmed maternal creatinine clearance <50mL/minute

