## Appendix V: General Management Guidelines for Maternal Increased Creatinine and Reduced Creatinine Clearance

Maternal Increased Creatinine and Reduced Creatinine Clearance		
CONDITION AND SEVERITY	STUDY DRUG USE	FOLLOW-UP AND MANAGEMENT
All grades		
 
Assess participant for other potential causes of decreased renal function per site standard of care.
 
Management action should be taken based on the absolute value of each participant's creatinine value and estimated CrCl (not change from study baseline).
 
Management should be based on the most severe result (creatinine or creatinine clearance).
 

Grade 1 increased creatinine	Continue study drug	Follow-up per SOE
Grade 2 increased creatinine OR reduced creatinine clearance (estimated CrCl <90 to $\geq 60$ mL/min)	Continue study drug	
Repeat the test and perform urinalysis within 1 week of site awareness.
 
 
If the repeat test does not confirm Grade 2 severity, follow the management guidance for that severity grade.
 
If the repeat test confirms Grade 2 severity: 
 
Inform the CMC, and
 
Monitor creatinine and CrCl every 2 weeks until creatinine and CrCl are stable or improving, and
 
Update the CMC with each new result
 
 
 

Grade 3 or Grade 4 increased creatinine OR reduced creatinine clearance (estimated CrCl <60mL/min)	Hold study drug while awaiting confirmatory test result.	
Repeat the test and perform urinalysis within 3 business days of site awareness.
 
 
If the repeat test does not confirm Grade 3 or Grade 4 severity: 
 
Resume study drug at the site clinician's discretion, and
 
Follow the management guidance for that severity grade
 
 
 
If the repeat test confirms Grade 3 or Grade 4 severity: 
 
Inform the CMC, and
 
Permanently discontinue study drug, and
 
Monitor creatinine and CrCl at the frequency set by the CMC, and
 
Update the CMC with each new result
 
 
 

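### Permanent-stop rules disagree: Section 8.3 and Appendix V set different creatinine clearance limits (50 and 60 mL/min), and Section 8.3 and Appendix IV differ on re-challenge after a related Grade 4 laboratory event

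*Protocol*

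**What the plan says.** **Renal results.** Section 8.3 is mandatory in wording. Its last bullet names "Confirmed maternal creatinine clearance <50mL/minute" as a reason to end study drug permanently. Appendix V has a row headed "Grade 3 or Grade 4 increased creatinine OR reduced creatinine clearance (estimated CrCl <60mL/min". Drug is held at the first such result and the test is repeated. If the repeat confirms Grade 3 or 4, the instruction is "Permanently discontinue study drug, and" to keep monitoring and inform the CMC. That row sets no condition on relatedness and gives no recovery window. The row above it, under which drug continues, ends at 60 mL/min.

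**Which text applies.** Section 8.1.1 points to Appendix V "for detailed guidance on management of reduced creatinine clearance. All other adverse events should be managed as shown in" Appendix IV. Section 8.1.2 says that Appendix V "provides general guidance for management of the FTC/TDF in response to reduced creatinine clearance". Section 8.3 refers to neither appendix. For the PrEP Comparison Component, Section 7.3.3 says that "grading of creatinine and CrCl should be based on absolute value only, not on percentage change from baseline".

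**Other laboratory results.** Section 8.3 also requires a permanent stop for "Confirmed maternal Grade 4 laboratory abnormality related to study drug", with no exception for recovery. For Grade 3 it requires a stop only for a confirmed "Grade 3 laboratory abnormality related to study drug that does not resolve to Grade 2 or lower within 14 days of study drug hold". Appendix IV's Grade 4 laboratory row holds drug, repeats the test, stops permanently if the result has not come down to Grade 2 or below in 14 days, and otherwise lets re-challenge be considered with the CMC. It does not mention relatedness. The Grade 3 laboratory row in the same table separates related from unrelated events.

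**The concern.** A permanent-stop rule should give a site one answer for one result. Here two pairs of texts give different answers, and the protocol does not say which prevails.

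The renal case is the more important one. Section 13.5.4 lists new or worsening kidney damage as a rare but serious effect of this drug, and the women are pregnant or breastfeeding. A site with a confirmed CrCl of 55 mL/min finds a permanent stop in Appendix V and a limit of 50 in Section 8.3. In the Grade 4 case, a site and the CMC could consider restarting drug under Appendix IV in a woman for whom Section 8.3 has already required a permanent stop.

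What is at stake is participant safety and uniform conduct across sites. The estimates are hardly touched.

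**Working it through.** No sample size, power or alpha figure is involved. The check sets the stop rules side by side, with "confirmed" assumed throughout.

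| Confirmed result | Section 8.3 | Appendix | Same answer? |
|---|---|---|---|
| CrCl below 50 | Stop | V: stop | Yes |
| CrCl 50 to under 60 | CrCl bullet not met; Grade 3 bullet stops only if related and unresolved after 14 days of hold | V: stop, no conditions | No |
| CrCl 60 to under 90 | CrCl bullet not met | V: continue, monitor | Yes |
| Grade 4 laboratory (non-renal), related, recovers within 14 days | Stop | IV: re-challenge may be considered with the CMC | No |
| Grade 4 laboratory (non-renal), related, no recovery within 14 days | Stop | IV: stop | Yes |
| Grade 4 laboratory (non-renal), not related | Grade 4 bullet not met | IV alone applies | No competing instruction |

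**Renal rows.** Every value below 50 is also below 60, so a site that follows Appendix V never needs the limit of 50. The gap is the band from 50 to under 60. Take a confirmed CrCl of 55 judged unrelated, or one that recovers inside 14 days:

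- Appendix V requires a permanent stop.
- Section 8.3 requires none.
- Section 8.1.1 adds that unrelated laboratory events need not lead to interruption unless the investigator thinks it necessary.

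The same mismatch arises for a confirmed Grade 3 creatinine that is unrelated or recovers, and for an unrelated Grade 4 creatinine. Appendix V stops drug in each, and the Section 8.3 laboratory bullets do not.

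**Grade 4 rows.** The conflict is confined to events that are both related and recovered. Section 8.3's bullet on recurrence after re-challenge does not resolve it. That bullet can operate on Grade 3 events that settled or on unrelated Grade 4 events, and it makes no exception to the Grade 4 bullet.

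**How far a woman must fall.** Sections 4.2.1.6 and 4.2.3.3 require CrCl of at least 90 mL/min (at screening, or at the previous assessment for Step 2). From that floor:

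- to fall below 60: more than (90 − 60)/90 = 33.3%
- to fall below 50: more than (90 − 50)/90 = 44.4%

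These are minimum falls, because a woman starting above 90 must drop further.

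**Who could be subject to the rules.** Section 9.2.4 plans 233 women in Cohort 1 and 117 in Cohort 2. Those who may take drug number from 233 (no Step 2 entries) to 233 + 117 = 350 (all of Cohort 2 enters Step 2). This is the population under the rules, not a count of affected women. The documents give no on-study distribution of CrCl and no rate of related Grade 4 laboratory events, so that count cannot be computed.

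**Link to the analysis.** SAP 6.3.2 to 6.3.5 handle PrEP discontinuation by treatment policy, so the safety comparisons do not depend on the stop date. SAP 6.1, 6.2 and 6.3.1 use a while-on-treatment strategy and do depend on it. The first two belong to the PK Component, which is complete (Protocol Section 1.3.3.1). That leaves the adherence estimand in SAP 6.3.1.

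**The case against.** The best reply is that the renal texts do not contradict each other. Section 8.3 lists situations in which drug must stop; it does not say that these are the only ones, and it does not permit continuation between 50 and 60. A site that stops at 60 satisfies both texts, and Section 8.1.1 already says which table to use for reduced CrCl. This stands as far as it goes: applying the stricter rule reconciles them. But none of these sections says to apply the stricter rule, and the mandatory wording sits in Section 8.3 while the stricter limit sits in a table called general guidance.

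A reader might go further and infer that the limit of 50 is a dead letter because Appendix V governs. The documents do not settle that. On the wording of Section 8.1.2, 50 can equally be read as a hard floor beneath stricter guidance, and that uncertainty is the point.

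On Grade 4 events, the reply is that Appendix IV is merely silent on relatedness, that re-challenge is only a possibility requiring CMC consultation, and that the mandatory rule in Section 8.3 limits that discretion. This narrows the problem to related events that recover, but does not remove it: the Grade 3 row draws the related/unrelated distinction explicitly and the Grade 4 row does not.

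**Conclusion.** The inconsistency is real and minor. The renal texts differ for a confirmed CrCl of 50 to under 60 mL/min, and for confirmed Grade 3 or 4 creatinine where Section 8.3 adds conditions that Appendix V lacks. The laboratory texts differ for a confirmed, related Grade 4 event that recovers within 14 days.

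Few women are likely to be affected. That judgement rests on the entry floor of 90 mL/min and on the protocol's background figure of 2 confirmed Grade 2 or higher renal chemistry events among 424 women in one arm of an earlier trial (2/424 = 0.5%). That figure comes from women with HIV on a three-drug regimen followed to 14 days postpartum, so it indicates rarity and is not an estimate for this study.

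Two stronger readings are not supported. A reader might infer that women will be left on drug with failing kidneys. However, Appendix V holds drug at the first CrCl below 60, Appendix IV holds it at the first Grade 4 result, and the CMC is informed of confirmed results. A reader might also infer that the safety results are at risk. They are not, because those estimands use treatment policy. Any effect would be on which visits count in the adherence estimand, and with few women it is negligible.

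**What to change.** Two edits are enough.

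1. Replace the last bullet of Section 8.3 with: *Confirmed maternal creatinine clearance <60 mL/min or confirmed Grade 3 or 4 creatinine, regardless of relatedness, per Appendix V.* With that bullet in place, the general Grade 3 and Grade 4 laboratory bullets need no separate renal exception.
2. In the Grade 4 laboratory row of Appendix IV, limit re-challenge to events assessed as not related, so that the row agrees with the mandatory rule in Section 8.3. If the team would rather allow CMC-approved re-challenge after a related event, it should amend Section 8.3 to say so. Keeping the stricter rule is the more cautious choice in this population.

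A clarification memo or letter of amendment would do this. There is no statistical cost: no sample size, estimand or analysis changes.

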## **9 STATISTICAL CONSIDERATIONS**

### **9.1 PK Component**

#### **9.1.1 General Design Issues-PK Component**

The IMPAACT 2009 PK Component aims to establish drug thresholds for adequate adherence in pregnancy and postpartum when FTC/TDF is administered daily during pregnancy and in the postpartum period under directly observed conditions. All maternal participants will be administered once daily FTC/TDF. All doses will be directly observed for the 12-week duration. DBS specimens will be collected at weekly intervals for analysis. Approximately 40 maternal participants will be recruited to obtain at least 30 evaluable maternal participants with 20 participants who are recruited in the antepartum group (14-24 weeks of gestation), and 20 who are recruited in the postpartum group (6-12 weeks postpartum). A maternal participant is considered evaluable if she fulfils the following criteria; a) completes PK Component follow-up, b) has adequate documentation that PrEP doses were directly observed, c) has demonstrated adequate adherence to PrEP, defined as no more than 12 total directly observed doses missed over 12 weeks (maternal participants with more than three consecutively missed doses will be reviewed by the CMC to determine evaluability), and (d) had adequate DBS samples shipped to the PK testing laboratory, defined as no more than one missed specimen in any given two-week interval over 12 weeks with a minimum of seven samples correctly collected, processed, handled and shipped. The rationale for this design is to collect as many weekly measurements as feasible to enable the most robust estimates, but also to allow flexibility for occasional missed visits and doses to enable practicability for participants and sites.

